6.3 Efficacy

Efficacy endpoints are assessed by as-randomized treatment group.

Randomization is stratified using the RTSM system, but analyses use the imputed randomization stratum, which is based primarily on the actual data (i.e., history of clinically relevant CV disease; see Section 6.2.5.1). The rationale for using the actual data in analyses is that sites may erroneously report the wrong stratum in the RTSM system. Hence, treatment group comparisons of binary efficacy endpoints are stratified by the imputed randomization stratum except within subgroups. If there are sparse data within a stratum, then results may be presented unstratified. Note that the phrase “randomization stratum” refers to the imputed randomization stratum throughout this section.

For binary efficacy endpoints, CIs are based on a normal approximation to the binomial distribution using asymptotic standard error (ASE). For continuous efficacy endpoints, CIs are based on the normal distribution. All CIs are 2-sided.

See Sections 7.2 and 7.3 for the definition of efficacy analysis periods and study days.

Efficacy Endpoints During the DBT Phase

During the DBT Phase, select endpoints are assessed over time at all scheduled time points postdose: 15, 30, 45, 60, and 90 minutes; 2, 3, 4, 6, 8, 24, and 48 hours.

Analyses are based on the DBT efficacy analysis set with eDiary measurement dates in the DBT Phase analysis period at planned time points of 15 minutes through 48 hours from the eDiary Migraine question category (see Section 7.4.2).

Efficacy Endpoints During the OLE Phase

Analyses are based on the OLE migraine analysis set with eDiary measurement dates in the OLE Phase analysis period from the eDiary Migraine question category (see Section 7.4.2).

Methods of Handling Missing Data

Methods of handling missing data in analyses of binary efficacy endpoints during the DBT Phase are defined as follows:

- Noncompleter = Failure (NC=F): Subjects with missing data at a single time point are classified as failures. This missing data imputation method is applied to endpoints based on data from a single time point (e.g., primary endpoint) as the main analysis method.
- Noncompleter Missing Data at More Than 1 Time Point = Failure (NC1=F): Subjects with missing data at >1 time point postdose in a specified time period are classified as failures. This missing data imputation method is applied to endpoints that are based on data from multiple time points (e.g., key secondary endpoint of sustained headache pain freedom from 2 to 24 hours postdose) as the main analysis method.
- Multiple imputation (see Section 6.3.2.2). This missing data exclusion method is applied only to the primary endpoint as a sensitivity analysis.
- Varying response rate imputation (see Section 6.3.2.2). This missing data exclusion method is applied only to the primary endpoint as a sensitivity analysis.

Intercurrent Event of Rescue Medication Use

During the DBT Phase, the intercurrent event of DBT rescue medication use is handled using Rescue Medication = Failure (RM=F), which has 2 criteria:

- 1) Subjects who take DBT rescue medication at or before a nonmissing efficacy measurement at a postdose time point are classified as failures at that time point, for a given qualifying migraine attack.
- 2) Subjects who take DBT rescue medication at or before a postdose time point with a missing efficacy measurement are classified as failures at that time point, for a given qualifying migraine attack. This criterion is used only in sensitivity analyses based on data imputation (see Section 6.3.2.2), or analyses that present the rate of rescue medication use for a specific endpoint (e.g., pain relapse) in the DBT Phase.

The RM=F method applies to analyses of all binary efficacy endpoints, except those based on rescue medication use (see Section 7.5).

During the OLE Phase, use of acute migraine-specific rescue medication is part of the endpoint definition of continuous efficacy endpoints based on migraine days per month.

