5 SAMPLE SIZE, POWER, AND TYPE I ERROR

It is anticipated that about 90% of the 300 subjects randomized to each treatment group will have a migraine in the allotted time period of the DBT Phase, resulting in approximately 270 subjects evaluable for efficacy in each treatment group.

The sample size calculation is based on pooled results from Phase 3 single-dose migraine studies C4951054 (BHV3000-301), C4951055 (BHV3000-302), and C4951056 (BHV3000-303). Pooled response rates for migraine headache pain relief at 2 hours postdose were 57.9% for rimegepant 75 mg and 43.9% for placebo in these studies.

A total sample size of 540 evaluable subjects (270 per treatment group) will provide approximately 90% power for the primary endpoint of migraine headache pain relief at 2 hours postdose in the DBT Phase. This is based on a chi-square test with a 2-sided alpha level of 0.05, and assumes that the true response rates in the subjects unsuitable for triptan use is equivalent to the overall pooled response rates above.

Type 1 error is controlled using a 2-sided alpha level of 0.05 and hierarchical testing. First, the significance of the primary endpoint is evaluated at the 2-sided alpha level of 0.05 for rimegepant versus placebo. If the primary endpoint is not significant (i.e., $p\text{-value} > 0.05$), then any further tests on key secondary endpoints will have p-values presented only for descriptive purposes. If the primary endpoint is significant (i.e., $p\text{-value} \leq 0.05$), then the key secondary endpoints are tested hierarchically, each at a 2-sided alpha level of 0.05, in the order specified in Section 3.2.2.1. Thus, a key secondary endpoint is tested only if the preceding key secondary endpoint in the hierarchy is determined to be significant (i.e., $p\text{-value} \leq 0.05$). If a test in the hierarchy is not significant, then any further tests on endpoints in the sequence have p-values presented only for descriptive purposes, and no conclusions are drawn from those results.

For testing of other secondary or exploratory endpoints, no attempt is made to adjust for multiplicity. P-values are evaluated at an unadjusted, 2-sided alpha level of 0.05 and presented only for descriptive purposes.

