The overall summary table of treatment comparisons of all primary and key secondary efficacy endpoints during the DBT Phase is also produced by subgroup level for all efficacy subgroups of interest described in Section 4.3.1. Separate tables are provided for each subgroup. Analyses are performed unstratified, and p-values are presented only for descriptive purposes. Results support exploratory objectives #17 and #18.

Forest Plot of Primary and Key Secondary Efficacy Endpoints During the DBT Phase

The forest plot of treatment comparisons of all primary and key secondary efficacy endpoints during the DBT Phase is provided for the DBT efficacy analysis set, and is based on the overall summary. The plot displays the following statistics:

- Response rate (i.e., “n/N” and percentage) by treatment group
- Stratified percentage difference between treatment groups (rimegepant – placebo) and 95%CI.

Percentage differences with p-values that are determined to be significant based on the testing hierarchy are identified. Note that the plot displays results for no rescue medication use within 24 hours postdose so that positive percentage differences favor rimegepant for these key secondary endpoints.

By-Subject Listing of Primary and Key Secondary Efficacy Endpoints During the DBT Phase

The by-subject listing of primary and key secondary efficacy endpoints during the DBT Phase is provided for the full analysis set that includes first DBT rescue medication date/time (see Section 7.1), time to first DBT rescue medication use in hours (see Section 6.3.3.2), migraine headache pain intensity at the time of DB study drug dosing, MBS before DB study drug dosing, and reason(s) for exclusion from the DBT efficacy analysis set (randomized more than once; not treated with DB study drug; treated with DB study drug but no qualifying migraine attack at the time of DB study drug dosing; qualifying migraine attack at the time of DB study drug dosing but no postdose efficacy data in the DBT Phase); note that the last 3 reasons are mutually exclusive.

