6.3.5.1 Efficacy at All Scheduled Time Points Postdose During the DBT Phase

Analyses are based on the DBT efficacy analysis set.

The table of efficacy at each planned time point from 15 minutes through 48 hours postdose during the DBT Phase is provided separately for each of the following efficacy endpoints: pain relief, pain freedom, MBS freedom, return to normal function, photophobia freedom, phonophobia freedom, and nausea freedom. Results support exploratory objectives #3 through #9.

At each planned time point postdose, the percentage of subjects achieving the endpoint during the DBT Phase is compared between treatment groups using analogous methods as the main analysis of the primary endpoint with NC=F and RM=F (see Section 6.3.2.1). For endpoints defined below, “rescue medication” denotes DBT rescue medication.

The line plot of pain relief over time during the DBT Phase displays percentage of subjects achieving pain relief on the y-axis versus time in minutes on the x-axis by treatment group. Error bars denote ± 1 ASE.

Let X denote a planned time point postdose: 15, 30, 45, 60, or 90 minutes; 2, 3, 4, 6, 8, 24, or 48 hours.

Pain Relief Over Time

At time point X, subjects who meet both of the following criteria are classified as responders:

- Migraine headache pain intensity of none or mild at X, i.e., in the X analysis window
- No rescue medication taken at or before the migraine headache pain intensity measurement in the X analysis window (see Section 7.5).

At time point X, subjects who are not responders are classified as failures. Failure criteria include any of the following:

- Rescue medication taken at or before X (RM=F; see Section 7.5)
- Moderate or severe migraine headache pain intensity at X
- Missing migraine headache pain intensity at X (NC=F).

Pain Freedom Over Time

At time point X, subjects who meet both of the following criteria are classified as responders:

- Migraine headache pain intensity of none at X, i.e., in the X analysis window
- No rescue medication taken at or before the migraine headache pain intensity measurement in the X analysis window (see Section 7.5).

At time point X, subjects who are not responders are classified as failures. Failure criteria include any of the following:

- Rescue medication taken at or before X (RM=F; see Section 7.5)
- Mild, moderate, or severe migraine headache pain intensity at X
- Missing migraine headache pain intensity at X (NC=F).

MBS Freedom Over Time

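### SAP 6.3 plans Wald intervals for every binary efficacy endpoint with no small-count alternative; single-arm intervals fail in cells with very few responders or non-responders

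*SAP*

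**What the plan says.** SAP 6.3 sets one interval method for binary efficacy endpoints: "CIs are based on a normal approximation to the binomial distribution using asymptotic standard error". It adds that "All CIs are 2-sided". The only provision for thin data is "If there are sparse data within a stratum, then results may be presented unstratified", which drops the stratification and leaves the interval formula as it was.

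Three planned outputs carry this method into cells that may hold few events:

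- **Subgroup tables (SAP 6.3.1.1).** All primary and key secondary endpoints are repeated by CV history and by triptan-failure history. "Analyses are performed unstratified, and p-values are presented only for descriptive purposes". Protocol 7.1.6 caps the CV stratum at 15% of those randomized.
- **Time-point tables (SAP 6.3.5.1).** "The table of efficacy at each planned time point from 15 minutes through 48 hours postdose during the DBT Phase" is produced for seven endpoints, among them pain freedom, by the method of the main analysis.
- **Pain relapse (SAP 6.3.5.3).** Rescue rates with 95% intervals are shown by CV stratum and arm, only among subjects who were pain-free at 2 hours.

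SAP 6.1.2 sends the reader to a Core SAP, which is not among the documents, for descriptive statistics. The interval method for binary efficacy endpoints is nevertheless fixed in SAP 6.3 itself.

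**The concern.** A Wald interval takes its width from the observed proportion. When that proportion is 0 or 1, the estimated standard error is 0 and the printed 95% interval is a single point. With one to three responders among 40, the lower limit is negative. In both situations the interval does not have the confidence level printed beside it.

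What is at stake is how the descriptive tables are read. Their p-values carry no inferential weight, so the interval is the main statement of uncertainty. A cell of 0/40 printed with limits of 0% and 0% tells the reader that the rate is known exactly, when the data are compatible with several percent.

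**Working it through.** **Inputs from the documents**

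- Evaluable size: 90% of 300 randomized per arm, "resulting in approximately 270 subjects evaluable for efficacy in each treatment group" (SAP 5).
- Pain relief at 2 hours: pooled rates of "57.9% for rimegepant 75 mg and 43.9% for placebo in these studies" (SAP 5).
- Power calculation: "This is based on a chi-square test with a 2-sided alpha level of 0.05".
- CV cap: 15% of about 600 (Protocol 7.1.6).

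**The plan's own figure.** With n=270 per arm, rates of 0.579 and 0.439 and mean rate 0.509, normal-approximation power is Φ{[0.140·√270 − 1.96·√(2·0.509·0.491)] / √(0.579·0.421 + 0.439·0.561)} = 0.904. The stated power of about 90% reproduces. The documents state no interval coverage to compare against.

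**Size of the CV subgroup.** 600 × 0.15 = 90 randomized, or 45 per arm. 45 × 0.90 = 40.5, so about 40 evaluable per arm.

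**Formulas, for x responders among n and p̂ = x/n**

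- Wald: p̂ ± 1.96·√[p̂(1−p̂)/n].
- Wilson: [p̂ + z²/2n ± z·√(p̂(1−p̂)/n + z²/4n²)] / (1 + z²/n), with z = 1.96.
- Coverage at true rate p: the sum of binomial probabilities over all x whose interval contains p (exact, no simulation).

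**One case in full: n=40, p=2% (assumed).** The Wald interval at x=0 is 0 to 0 and misses. At x=1 it is −2.3% to 7.3%, and x=1 to 4 all contain 2%. Those four outcomes have probabilities 0.364 + 0.145 + 0.037 + 0.007 = 0.553, which is the coverage. Almost all of the loss is the 0.98⁴⁰ = 0.446 chance of no responder.

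**Single-arm coverage.** The documents give no rates for the exposed cells, so every rate below is an assumption except 43.9% and 57.9%.

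| n per arm | True rate | Expected responders | Wald | Chance of 0 responders | Wilson |
|---|---|---|---|---|---|
| 40 | 2% | 0.8 | 55.3% | 44.6% | 95.4% |
| 40 | 5% | 2.0 | 86.8% | 12.9% | 95.2% |
| 40 | 10% | 4.0 | 91.5% | 1.5% | 94.3% |
| 40 | 43.9% | 17.6 | 94.5% | 0% | 94.5% |
| 40 | 57.9% | 23.2 | 92.3% | 0% | 94.5% |
| 270 | 0.5% | 1.4 | 74.1% | 25.8% | 95.2% |
| 270 | 1% | 2.7 | 93.2% | 6.6% | 94.4% |
| 270 | 2% | 5.4 | 90.4% | 0.4% | 94.9% |
| 270 | 5% | 13.5 | 91.7% | 0% | 95.2% |

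At n=40 and 5%, there is a further 73% chance (x = 1, 2 or 3) that the lower limit is negative.

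**Pain-relapse cell.** If 20% are pain-free at 2 hours (assumed), the CV stratum has 40 × 0.20 = 8 subjects per arm. For rescue rates of 5%, 10%, 20% and 30%, Wald coverage is 34%, 56%, 82% and 93%.

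**A result that needs no assumed rate.** For 0/40, Wald gives 0 to 0 and Wilson 0 to 8.8%. For 0/270, Wald gives 0 to 0 and Wilson 0 to 1.4%.

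**Differences between arms**

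| n per arm | Rates | Wald | Newcombe |
|---|---|---|---|
| 40 | 57.9% vs 43.9% | 94.3% | 94.5% |
| 40 | 20% vs 10% | 94.0% | 95.9% |
| 40 | 10% vs 3% | 92.0% | 96.7% |
| 40 | 5% vs 2% | 86.3% | 98.7% |
| 270 | 0.5% vs 0.5% | 97.5% | 99.3% |

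**Primary comparison.** Simulated coverage of the stratified risk difference, with strata of 230 and 40 per arm, is 94.4%.

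**The case against.** The strongest reply is that little depends on these intervals. CV-subgroup efficacy is an exploratory objective, its p-values are descriptive, and the time-point results other than the 2-hour endpoints lie outside the testing hierarchy (SAP 6.3.5). The tables print n/N, so a reader can see a zero count. All of this stands, and it keeps the point minor. It does not make a zero-width 95% interval correct.

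The low rates are also assumed. The documents give response rates for 2-hour pain relief only, and none for early time points, sustained or functional endpoints, or any subgroup. This stands too. The coverage figures show what happens if rates are low; they do not predict that they will be.

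Three stronger readings are tempting, and the documents do not support them:

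- **That the CV tables as a whole fall far short of 95% because the subgroup is small.** At 40 per arm and the plan's own pain-relief rates, coverage is 92% to 95%. The failure comes from low counts.
- **That between-arm differences fail in the same way.** At n=40 they are only mildly affected unless rates are very low. When both arms are equally near zero, the difference over-covers.
- **That 40 per arm is a firm ceiling.** The cap applies at randomization through the randomization system. The analysed subgroup uses the imputed stratum, which rests primarily on case report form data (SAP 6.2.5.1), so its size may differ somewhat.

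**Conclusion.** Wrong as written, but only for low-count cells. Where roughly fewer than 2 to 3 responders or non-responders are expected in an arm, the planned single-arm interval can cover 55% to 87% instead of 95%, on the assumed rates shown. At 0% or 100% it has zero width whatever the true rate. Above that range the shortfall is a few points: about 90% to 93% at n=270 for rates of 1% to 5%. Differences at n=40 drop materially only at very low rates.

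A reader might infer that the trial's main conclusion is at risk. It is not. The primary stratified comparison covers about 94%, the stated power reproduces, and no multiplicity-controlled claim depends on the affected subgroup and early time-point intervals. The zero-width result is certain. How often it would appear depends on rates that the documents do not give.

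**What to change.** Amend the interval paragraph of SAP 6.3 as follows:

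1. Use Wilson score intervals for all single-arm percentages of binary efficacy endpoints.
2. Use Newcombe or Miettinen-Nurminen intervals (name one) for the unstratified subgroup differences of SAP 6.3.1.1.
3. Keep the stratified Mantel-Haenszel differences, intervals and p-values unchanged, including those in the full-set time-point tables.

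Apply the rule to every cell, without a switch at low-rate time points. A switch without a set threshold would choose the method after the data are seen, and would mix methods within one stratified table.

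The cost is a small programming change and intervals that are asymmetric and in places slightly wider. Newcombe is conservative at very low rates (98.7% at 5% vs 2%, n=40). A subgroup interval and its descriptive p-value could occasionally disagree about zero, so the SAP should name the p-value method. A stratified time-point difference with no responders in either arm would still have zero width, but the Wilson intervals beside it would show the uncertainty. No new data are needed, and sample size and type I error do not change.

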6.3.1 Overall Efficacy

6.3.1.1 Overall Summary of Primary and Key Secondary Efficacy Endpoints During the DBT Phase

Overall Summary Table of Primary and Key Secondary Efficacy Endpoints During the DBT Phase

The overall summary table of treatment comparisons of all primary and key secondary efficacy endpoints during the DBT Phase tested hierarchically is provided for the DBT efficacy analysis set, and presents the following statistics:

- Response rate (i.e., “n/N” and percentage) and 95% CI for each treatment group
- Stratified percentage difference between treatment groups (rimegepant – placebo), 95% CI, and p-value.

Analyses are based on main methods described in Section 6.3.2.1. Key secondary efficacy endpoints are displayed in the order presented in Section 3.2.2.1. P-values that are determined to be significant based on the testing hierarchy are identified.

If the main analysis of the primary endpoint is significant (p-value ≤ 0.05 ; see Section 6.3.2.1), then the key secondary endpoints are tested hierarchically, each at a 2-sided alpha level of 0.05, in the order specified in Section 3.2.2.1. Thus, a key secondary endpoint is tested only if the preceding key secondary endpoint in the hierarchy is determined to be significant (i.e., p-value ≤ 0.05). If a test in the hierarchy is not significant, then any further tests on endpoints in the sequence have p-values presented only for descriptive purposes, and no conclusions are drawn from those results.

If the main analysis of the primary endpoint is not significant (i.e., p-value > 0.05), then any further tests of key secondary endpoints will have p-values presented only for descriptive purposes, and no conclusions are drawn from those results.

For each comparison, the null hypothesis of interest H_0 is that the percentage of responders observed on rimegepant (denoted $p_{\text{rimegepant}}$) is equal to the percentage observed on placebo (denoted p_{placebo}), i.e., $H_0: p_{\text{rimegepant}} = p_{\text{placebo}}$. The alternative 2-sided hypothesis of interest H_1 is that the rates of responders observed on rimegepant and placebo differ, i.e., $H_1: p_{\text{rimegepant}} \neq p_{\text{placebo}}$.

The overall summary table of treatment comparisons of all primary and key secondary efficacy endpoints during the DBT Phase is also produced by subgroup level for all efficacy subgroups of interest described in Section 4.3.1. Separate tables are provided for each subgroup. Analyses are performed unstratified, and p-values are presented only for descriptive purposes. Results support exploratory objectives #17 and #18.

Forest Plot of Primary and Key Secondary Efficacy Endpoints During the DBT Phase

The forest plot of treatment comparisons of all primary and key secondary efficacy endpoints during the DBT Phase is provided for the DBT efficacy analysis set, and is based on the overall summary. The plot displays the following statistics:

- Response rate (i.e., “n/N” and percentage) by treatment group
- Stratified percentage difference between treatment groups (rimegepant – placebo) and 95%CI.

Percentage differences with p-values that are determined to be significant based on the testing hierarchy are identified. Note that the plot displays results for no rescue medication use within 24 hours postdose so that positive percentage differences favor rimegepant for these key secondary endpoints.

By-Subject Listing of Primary and Key Secondary Efficacy Endpoints During the DBT Phase

The by-subject listing of primary and key secondary efficacy endpoints during the DBT Phase is provided for the full analysis set that includes first DBT rescue medication date/time (see Section 7.1), time to first DBT rescue medication use in hours (see Section 6.3.3.2), migraine headache pain intensity at the time of DB study drug dosing, MBS before DB study drug dosing, and reason(s) for exclusion from the DBT efficacy analysis set (randomized more than once; not treated with DB study drug; treated with DB study drug but no qualifying migraine attack at the time of DB study drug dosing; qualifying migraine attack at the time of DB study drug dosing but no postdose efficacy data in the DBT Phase); note that the last 3 reasons are mutually exclusive.

Results for each binary endpoint are based on the NC=F and RM=F analysis methods, except for key secondary endpoint #2. Results for each endpoint are abbreviated as follows: “R” for responder; “F” for failure; “N/A” for not applicable for key secondary endpoints #3, 4, and 5 for the DBT analysis set with functional disability level of normal at the time of DB study drug dosing; and missing (blank) for subjects excluded from the DBT efficacy analysis set.

